4.7.3.2 Therapeutic Response

1) Definition:

Relapse will be assessed according to the response criteria of the International Working Group shown in the protocol, Table 7.2.1.1-1. Relapse will be judged by the investigator in the site (Site judgment) and by Central Pathological Reviewer (Central judgment) and recorded in eCRF.

2) Analysis Set:

FAS, PPS

3) Analysis Method:

- A summary of the number and percentage of subjects judged as Relapse by both Central judgment and Site judgment will be calculated.

4.8 Safety Evaluation

4.8.1 Extent of Exposure

1) Definition:

Duration of exposure to treatment (days), full dose of OCV-501, total number of doses

2) Analysis Set:

SS

3) Analysis Method:

A summary of the descriptive statistics will be calculated by treatment arm.

Duration of exposure to treatment will be calculated in days as follows:

$$\text{IMP administration end date} - \text{IMP administration start date} + 1$$

4.8.2 Adverse Events

1) Definition:

AEs will be coded using the Medical Dictionary for Regulatory Activities (MedDRA version 20.1). Severity will be graded using Common Terminology Criteria for Adverse Events (CTCAE) version 4.03.

Treatment-emergent AEs (TEAE) are defined as those AEs that either start or worsen in severity on or after the date/time of first dose of IMP administration. TEAEs will be tabulated by SOC and PT with PT substituted for verbatim terms.

An adverse drug reaction (ADR) is defined as a response to a drug which is noxious and unintended, and which occurs at doses normally used in man for the prophylaxis, diagnosis, or therapy of disease, or for the modifications of physiological function (WHO definition). In this study, AEs with causal relationship (Definitely related, Probably related, Possibly related) are considered as ADR (potentially drug related AEs).

When dates are missing or partially missing, AEs will be assumed to be treatment-emergent, unless there is clear evidence to suggest that the AE started prior to the first dose of IMP administration.

Also, serious adverse event (SAE), death and AE leading to discontinuation will be considered separately.

2) Analysis Set:

SS

3) Analysis Method:

All TEAE summaries will describe the number of subjects reporting at least one AE and the total number of events reported. These will generally include the following summaries:

- A summary of the number and percentage of subjects reporting a TEAE or ADR by treatment arm, SOC and PT
- A summary of the most common TEAEs or ADRs by treatment arm, SOC and PT (reported by $\geq 5\%$ of subjects in any treatment arm)
- A summary of the TEAEs by treatment arm and PT (reported by $\geq 5\%$ of subjects in any treatment arm)
- A summary of the number and percentage of subjects reporting a TEAE or ADR by treatment arm, CTCAE severity grade, SOC and PT
- A summary of the number and percentage of subjects reporting a TEAE by maximum CTCAE grade and PT (Category: All grade, Grade 1+2, Grade 3+4+5)
- A summary of the number and percentage of subjects reporting a TEAE or ADR leading to death by treatment arm, SOC and PT
- A summary of the number and percentage of subjects reporting a serious TEAE by treatment arm, SOC and PT

- A summary of the number and percentage of subjects reporting a TEAE or ADR leading to discontinuation by treatment arm, SOC and PT
- A summary of all the summaries above

For by-severity summaries, for each subject reporting multiple AEs, the worst severity recorded will be used.

By-subject listings of all AEs (including non-treatment-emergent events) will be generated. These will include the following.

- A by-subject listing of all deaths that occurred during the study
- A by-subject listing of all SAEs other than death
- A by-subject listing of all AEs leading to discontinuation of IMP administration

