9.2 Criteria and Procedures for Withdrawal of Individual Subjects

In any of the events listed below, the investigator or subinvestigator will discontinue IMP administration, perform the tests to be performed at withdrawal stipulated in Section 7.1, Schedule and Procedures of the Trial, and promptly inform the sponsor of the withdrawal (Annex 1, Emergency Contact). The investigator or subinvestigator will record the date and reason for withdrawal in the CRF.

If withdrawal is necessitated by problems with safety, such as the occurrence of an AE or aggravation of the underlying disease, the investigator or subinvestigator will promptly take appropriate measures and perform follow-up if necessary (refer to Section 8.4, [Follow-up Investigation of Adverse Events](#)).

- 1) If the patient wishes to withdraw from the trial
- 2) If the investigator or subinvestigator judges that it is difficult to continue IMP administration due to occurrence of an AE
- 3) If relapse of the primary disease (AML) is observed
- 4) If a prohibited concomitant drug or therapy is used
- 5) If it is later found that the patient did not to meet the eligibility criteria at the time of enrollment
- 6) If the patient is found to be pregnant
- 7) If it is not possible to administer the IMP within 21 days after obtaining informed consent
- 8) If the investigator or subinvestigator judges that it is necessary to discontinue IMP administration for any another reason

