2 TRIAL OBJECTIVES

The primary objective is to compare the disease-free survival (DFS) in AML patients 60 years or older, who are randomly assigned to receive either OCV-501 monotherapy or placebo.

The secondary objectives are:

- To compare overall survival (OS) between both treatment arms
- To compare patient quality of life (QOL) (European Organization for Research and Treatment of Cancer [EORTC] QLQ-C30) and performance status (PS; Eastern Cooperative Oncology Group performance status [ECOG PS]) between both treatment arms
- To characterize and compare safety in both treatment arms
- To assess immunological responses (OCV-501 specific interferon gamma [IFN- γ] production, WT1-killer peptide specific IFN- γ production, anti-OCV-501 antibody level, anti-WT1 antibody level, immunoglobulin)
- To assess WT1 mRNA level

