4.12 Determination of Sample Size

The number of AML patients is not very high, and is estimated to be approximately 7000 in Japan⁷. From the fact that in the previous clinical trial (JALSG GML200) in elderly AML patients, it has been forecast that the possible enrollment in Japan is to be at most 70 in one year. Also, from the preliminary trial feasibility survey, it is known that around 50 subjects could be recruited in one year in the Republic of Korea and Taiwan. Through a global trial in Japan, the Republic of Korea and Taiwan, it is considered possible to enroll 120 subjects in one year to assess the efficacy of OCV-501.

Within the limitation of the past experiences with regard to IMP administration, the target sample size will be considered with reference to following publications.^{5,6,7,9} With reference to disease-free survival which has been reported from trials in AML patients 60 years or older who have received the consolidation therapy followed by maintenance therapy, the 2-year DFS rate of placebo arm has been estimated to be around 20%.^{5,6,7}

On the other hand, considering the so-called graft-versus-leukemia (GVL) effect associated with a lower relapse risk after the allogeneic hematopoietic stem cell transplantation, OCV-501 is basically expected to have the same benefits. With reference to the findings of Kurosawa et al,⁹ which have reported a 30% higher 2 or 3-year DFS in elderly AML subjects who have received the allogeneic hematopoietic stem cell transplantation compared with those without transplantation, OCV-501 is expected to have a 15% - 20% higher 2-year DFS. Under the assumption of exponential distribution of DFS time, the hazard ratio (placebo vs. OCV-501) has been set to 0.57 - 0.65, and with a two-sided log-rank test at the 5% significance level, 60 or more subjects in each treatment group can achieve a power of 53% - 75% or more to detect the difference between placebo and OCV-501 groups.

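### AE tables in SAP 4.8.2 make no allowance for time at risk although AE observation tracks DFS; exposure-adjusted rates and an early-window table would be a cheap addition

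*SAP*

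**What the plan says.** Comparing safety is a secondary objective: "To characterize and compare safety in both treatment arms" (SAP 2). For AEs, SAP 4.8.2 lists tables such as "A summary of the number and percentage of subjects reporting a TEAE or ADR by treatment arm, SOC and PT", with similar tables for serious TEAEs and for events leading to death or discontinuation. Each TEAE summary also reports the total number of events. Protocol 11.3.2 likewise tabulates subjects and occurrences per arm. SAP 4.2 makes the count of non-missing observations the denominator of every percentage.

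Exposure is a separate descriptive table by arm: "Duration of exposure to treatment (days), full dose of OCV-501, total number of doses" (SAP 4.8.1). No analysis in SAP 4.8.2, 4.9 or 4.11 joins it to the AE counts. A person-year rate with a 95% CI is defined in SAP 4.7.1.1, but only for DFS and, by reference, OS.

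The reasons for stopping study drug in Protocol 9.2 include "If relapse of the primary disease (AML) is observed". The withdrawal examination then takes place within 7 days (Protocol 7.1.4.2) and closes the individual trial period (Protocol, Definitions of Terms). After it, Protocol 8.2.2 and 8.4 provide only for follow-up of unresolved AEs and for SAEs whose relationship to study drug cannot be excluded. SAP 4.8.2 gives the start of the TEAE window but not its end.

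**The concern.** How long a subject is observed for AEs depends on the primary efficacy outcome. If the arms differ in DFS, they also differ in the time during which an AE can be recorded. A crude percentage then mixes the risk of an event with the opportunity to observe it. Total event counts have the same weakness to a greater degree, because they scale directly with observation time.

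At stake is the reading of the safety comparison. If the drug prolongs DFS, part of an AE excess may be only longer observation. If it shortens DFS, part of a real excess may be hidden. The tables of events reaching 5% of subjects in either arm are affected too, since longer observation brings more terms over the threshold.

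**Working it through.** **Inputs (SAP 4.12).** Placebo: "the 2-year DFS rate of placebo arm has been estimated to be around 20" percent. Gain: "OCV-501 is expected to have a 15% - 20% higher 2-year DFS", so 35% to 40%. DFS is taken as exponential. Effect size: "the hazard ratio (placebo vs. OCV-501) has been set to 0.57 - 0.65". The arms have 60 subjects each and are compared by a log-rank test at two-sided alpha 0.05.

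**The plan's own figures first.**
- HR = ln(0.35)/ln(0.20) = 0.652 and ln(0.40)/ln(0.20) = 0.569. These match 0.65 and 0.57, read numerically as OCV-501 relative to placebo.
- Expected events with 2 years per subject: 60 × 0.80 + 60 × 0.65 = 87, and 60 × 0.80 + 60 × 0.60 = 84.
- Schoenfeld power = Φ(½√D·|ln HR| − 1.96) = 51.3% and 73.3%, within 2 points of the stated 53% and 75%.

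The design model is therefore understood and can be used for time at risk.

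**Observation time.** λ = −ln S/2, and mean time to relapse, death or 2 years = (1 − S)/λ.
- Placebo: λ = 0.805; 0.80/0.805 = 0.994 years (363 days).
- OCV-501 at 35%: λ = 0.525; 0.65/0.525 = 1.238 years (452 days), ratio 1.25.
- OCV-501 at 40%: λ = 0.458; 0.60/0.458 = 1.310 years (478 days), ratio 1.32.

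Total event counts at an equal constant AE rate would be inflated by the same 25-32%.

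**Crude incidence with no drug effect.** The documents give no AE rate. Assume a constant rate r per year, equal in both arms. Crude incidence = r/(r+λ) × (1 − exp(−2(r+λ))).

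| r per year | Placebo | OCV-501 (35%) | OCV-501 (40%) |
|---|---|---|---|
| 0.1 | 9.2% | 11.4% | 12.0% |
| 0.25 | 20.8% | 25.4% | 26.7% |
| 0.5 | 35.5% | 42.5% | 44.5% |
| 1 | 53.9% | 62.5% | 64.9% |
| 2 | 71.0% | 78.7% | 80.8% |
| 4 | 83.2% | 88.4% | 89.7% |

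The excess is 2 to 11 points. Choosing r = 0.396 to give 30% on placebo yields 36.2% and 38.0% on OCV-501; r = 0.866 takes 50% to 58.4% and 60.8%. Adding the 7-day withdrawal window changes the excess by at most 0.5 point. The first-event rate per person-year equals r in both arms, because the incidence above is r times the mean time to first event or end of observation.

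**Where the constant-rate assumption fails.**
- AEs accompanying relapse: Protocol 8.1.1 excludes bare relapse from AEs but includes associated comorbidity that meets the definition. If a fraction q of relapses or deaths brings a reportable AE, add q·λ/(r+λ) × (1 − exp(−2(r+λ))). At r = 0.25 and q = 0.3, incidence is 40.9% against 41.4%, an excess of 0.5 point. At q = 0.5 it is 54.3% against 52.1% or 51.2%, a reversal of 2 to 3 points. At r = 1 and q = 0.5 an excess of 3.3 to 4.1 points remains.
- AEs confined to the first 8 weeks: let W = 56/365.25 years, with AE rate a = 2.49 per year up to W and zero afterwards, equal in both arms. Crude incidence, from the formula above with W in place of 2, is 30.0% on placebo and 30.6-30.7% on OCV-501. Person-time to first event or end = (1 − exp(−(a+λ)W))/(a+λ) + exp(−(a+λ)W) × (1 − exp(−λ(2−W)))/λ = 0.700 years on placebo and 0.867 or 0.916 on OCV-501. The first-event rates are 42.8 against 35.3 or 33.6 per 100 patient-years. Here the percentages are nearly right, and the rates show a false 18-22% advantage for OCV-501.

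**The case against.** The best case for the plan is that its AE output is descriptive. The trial is an exploratory phase 2 study with 60 per arm, no AE hypothesis test and no safety threshold. Under the constant-rate model the artefact would reach nominal two-sided 5% in only about 6% to 24% of trials. Exposure is shown by arm, AEs are also listed by subject, and laboratory, vital-sign and ECG data are summarised by time point, so an imbalance in follow-up would be visible. Protocol and SAP agree with each other. All of this stands, and it limits the point to an improvement in reporting. It does not close the gap: seeing unequal exposure does not give an adjusted incidence by SOC and PT, which needs each subject's time to first event.

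A reader might infer more than the documents support:
- That AEs are compared only as crude percentages. Event counts are planned as well, though they are equally unadjusted.
- That AE collection stops at relapse. It runs to the withdrawal examination, and possibly related SAEs remain reportable later.
- That an effective OCV-501 would necessarily look less safe. That needs a real DFS difference and a roughly constant AE rate. The documents give neither AE rates nor AE timing, and the working shows event types for which the excess vanishes or reverses.
- That the comparison should move to person-year rates. The 8-week example shows that those rates can mislead more than the percentages.

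**Conclusion.** The point holds as a cheap improvement to the SAP; it is not an error or a contradiction. AE observation time tracks DFS, and no planned AE summary allows for it. At the planning assumptions OCV-501 subjects would be observed 25-32% longer, and crude incidence could be 2-11 points higher on OCV-501 with no true difference.

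That range rests on exponential DFS at the planned rates, an assumed constant AE rate of 0.1 to 4 per year equal in both arms, and no withdrawals other than for relapse or death. Such withdrawals are not quantified in the documents and would narrow the gap. The effect is zero if DFS does not differ and changes sign if OCV-501 shortens it. Because the bias varies by event type, crude tables alone cannot show which case applies. The primary analysis is unaffected.

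**What to change.** In SAP 4.8.2:
- Keep the percentages. Beside them, for TEAEs, ADRs and serious TEAEs, give subjects with a first event per 100 patient-years, counted from first dose to first event or to the completion or withdrawal examination, with a 95% CI by the SAP 4.7.1.1 formula. That formula divides by the number of events, so say how cells with no events will be shown.
- State the end of the TEAE window, so that numerator and denominator cover the same period.
- Add a table for a common early window, for example Weeks 1-8, which SAP 4.3.1 already uses for disposition, or an analysis of time to first AE.
- State that the measures will be interpreted together and that the comparison will not rest on the rates alone.

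The dates needed (first dose, AE onset, completion or withdrawal examination) are already collected. Conduct, sample size and primary analysis do not change. The cost is longer output, plus the constant-hazard assumption behind the rates, which the early-window table or time-to-first-AE analysis is there to check.

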4.8.3 Clinical Laboratory Evaluation

1) Definition:

A subject will be defined as having a treatment-emergent laboratory abnormality if any of the following conditions are satisfied for a specific laboratory parameter.

- A laboratory result within the normal range at baseline and either a result below the lower limit of the normal range or above the upper limit of the normal range at any post-baseline time point.
- A laboratory result below the lower limit of the normal range at baseline and a laboratory result above the upper limit of the normal range at any post-baseline time point.
- A laboratory result above the upper limit of the normal range at baseline and a laboratory result below the lower limit of the normal range at any post-baseline time point.

In addition, laboratory values will be graded using CTCAE version 4.03.

2) Analysis Set:

SS

3) Analysis Method:

The following summaries will be generated:

- A summary of each laboratory parameter and its change from baseline by treatment arm and time point

- Shift table of laboratory parameter (Urinalysis) at each post-baseline point
- A summary of the number and percentage of subjects experiencing low, normal and high values at baseline and at each post-baseline time point (shift table)
- A summary of the number and percentage of subjects with different CTCAE grades at baseline, at each post-baseline time point and worst grade in post-baseline (shift table)
- A summary of new or worsened laboratory abnormalities based on CTCAE Grades (Categories: all grades, Grade 1+Grade 2, Grade 3+Grade 4)
In this table, the worst grade observed in post-baseline are summarised. Patients with no change or better grade from baseline are not counted. 'New' abnormality means 'grade 0' at baseline and '>= grade 1' after baseline. All grade means '>= grade 1' after baseline.

By-subject listings of all laboratory data will be generated by treatment arm with reference range provided and abnormal values will be marked with flags (H/L, Gx).

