7.1.4.2 Time of Withdrawal and Withdrawal Examination

At the time of withdrawal, the following examinations, observations, and evaluations will be performed within 7 days from the day on which withdrawal was judged to be necessary. If the subject refuses to undergo any examinations at the time of withdrawal, or if the investigator or subinvestigator judges that any examinations cannot be performed due to an emergency or other circumstances (eg, SAE or relapse of AML), of the examination items specified for the time of withdrawal, only those items that can be performed will be performed. The date and results of observations, examinations, and evaluations, and the date of blood samplings will be recorded in the medical records and CRF.

- 1) Adverse event observation and a concomitant drug survey will be performed.
- 2) The investigator or subinvestigator will perform a medical interview.
- 3) Body weight will be measured.
- 4) Vital signs (blood pressure, pulse rate, and body temperature) will be measured.
- 5) 12-Lead ECG will be performed.
- 6) Blood sampling for a hematology test and peripheral blood smear preparation* will be performed.
- 7) Blood sampling for a blood biochemistry test will be performed.
- 8) A urine sample for urinalysis will be collected.
- 9) QOL (EORTC QLQ-C30) self-assessment by subjects will be performed.
- 10) Performance status (ECOG PS) will be measured.
- 11) Samples will be collected for measurement of WT1 mRNA expression level.
- 12) Blood sampling for measurement of OCV-501-specific IFN- γ production, WT1-killer peptide specific IFN- γ production, anti-OCV-501 antibody level, anti-WT1 antibody level, and immunoglobulin will be performed.

*: If leukemic blast cells appear in peripheral blood or if there is a clinically significant reduction in blood cell components, the investigator or subinvestigator will perform bone marrow aspiration, and prepare bone marrow smears.

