8.1 Definitions

8.1.1 Adverse Event

[ICH E2A guideline: Definition]

Any untoward medical occurrence in a patient or clinical investigation subject administered a pharmaceutical product and which does not necessarily have to have a causal relationship with this treatment.

An AE can therefore be any unfavorable and unintended sign (including an abnormal laboratory finding, for example), symptom, or disease temporally associated with the use of a medicinal product, whether or not considered related to the medicinal product.^a

For this trial, the term “medical product” is regarded as “IMP,” and to secure the safety of subjects, AEs occurring from consent to the start of IMP administration are included in the definition of AEs in addition to the definition given by ICH.

If an event, symptom, or sign existing at the time of acquisition of informed consent worsens after acquisition of informed consent, or if an AE occurring between the acquisition of informed consent and start of IMP administration worsens after administration of the IMP, the exacerbation will be treated as a new AE.

In this trial, relapse of AML without any related comorbidity will not be handled as an AE. In the case that a comorbidity with AML associated with clinical symptoms meets the definition of an AE, it will be reported as an AE.

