P-values greater than or equal to 0.001, in general, will be presented to three decimal places. However, if a p-value is only presented to four decimal places (by SAS) it will not be rounded again, but will be presented to four decimal places. P-values less than 0.001 will be presented as “<0.001”.

Two sided statistical tests with $\alpha=0.05$ will be performed to test the hypotheses.

95% Confidence intervals (CIs) will be presented to one more decimal place than the raw data. Multiplicity will not be adjusted.

All report outputs will be produced using SAS® version 9.3 or a later version in a secure and validated environment.

Baseline

Baseline is defined as the last available screening or pre-treatment assessment.

Allowance window

Assessments taken outside of protocol allowable windows will be included in the summaries according to the eCRF assessment recorded by the investigator.

Unscheduled assessments

Extra assessments (laboratory data, vital signs or exploratory items associated with non-protocol clinical visits or obtained in the course of investigating or managing AEs) will be included in listings but not summaries.

Discontinuation assessments

Discontinuation assessments will be summarized according to the eCRF assessments recorded by the investigator at the time of discontinuation, not otherwise specified.

Graphs

Graphs will be plotted by “day” or “month” or “Visit timepoint (week)” as specified in the shells.

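### The worst-grade haematology tables have no cut at AML relapse, so leukaemic cytopenia can be counted as treatment-emergent and can differ between arms because relapse does

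*SAP*

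**What the plan says.** SAP 4.8.3 plans a CTCAE shift table that includes the worst post-baseline grade, and a table of new or worsened abnormalities in which "the worst grade observed in post-baseline are summarised. Patients with no change or better grade from baseline are not counted". The same section opens with a normal-range definition: "A subject will be defined as having a treatment-emergent laboratory abnormality if any of the following conditions are satisfied for a specific laboratory parameter". Those conditions look at any post-baseline time point. Neither the definition nor the tables have a closing date, and neither mentions relapse.

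SAP 4.2 settles which visits feed the summaries. On the withdrawal visit it says: "Discontinuation assessments will be summarized according to the eCRF assessments recorded by the investigator at the time of discontinuation, not otherwise specified". Extra, unscheduled assessments "will be included in listings but not summaries". The withdrawal examination has its own column in the trial schedule (SAP Table 3.1.3-1), so it is not an extra assessment.

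On the clinical side, Protocol 9.2 lists "If relapse of the primary disease (AML) is observed" among the reasons to discontinue IMP and perform the withdrawal tests. Protocol 7.1.4.2 requires, within 7 days of the withdrawal judgment, "Blood sampling for a hematology test and peripheral blood smear preparation". For adverse events, by contrast, Protocol 8.1.1 says that "relapse of AML without any related comorbidity will not be handled as an AE".

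**The concern.** A fall in blood counts is part of how AML relapse presents. Protocol 1.1 describes AML as inhibiting normal haematopoiesis, and Protocol 7.2.1.1 makes a clinically significant fall in blood cell components a trigger for marrow aspiration. Subjects enter in remission, with neutrophils above 1,000/μL, platelets above 50,000/μL and no transfusion need (Protocol 5.2), so a fall at relapse can readily register as new or worsened. Other anti-cancer drugs are prohibited until the post-treatment examination ends (Protocol 6.2.1), so a low count at withdrawal after relapse is more likely to come from the disease than from salvage therapy.

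The worst-grade haematology rows therefore mix drug effect with disease. If OCV-501 reduces relapse, placebo collects more disease cytopenia, and a modest haematological effect of OCV-501 could be masked. If it does not, the same counts add noise to both columns.

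**Working it through.** **1. Does a post-relapse count enter the tables?**
- Relapse leads to withdrawal (Protocol 9.2).
- Withdrawal includes haematology (Protocol 7.1.4.2).
- Discontinuation assessments are summarised (SAP 4.2).
- The worst grade is taken over post-baseline values with no upper limit (SAP 4.8.3).

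So yes. This is an inference: 4.8.3 does not expressly say that the worst grade uses the withdrawal visit, but nothing excludes it.

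**2. The plan's own figures.** Protocol 11.5 and SAP 4.12 give 2-year DFS of about 20% on placebo, 15 to 20 points more on OCV-501 (35 to 40%), exponential times, a hazard ratio of 0.57 to 0.65, 60 per arm, two-sided 5%, and power of 53 to 75%.
- Hazard ratio: ln(0.35)/ln(0.20) = 0.652 and ln(0.40)/ln(0.20) = 0.569, as stated.
- Events by 2 years: placebo 60 × 0.80 = 48; OCV-501 60 × 0.65 = 39 or 60 × 0.60 = 36. Totals are 87 and 84.
- Power (Schoenfeld), Φ(√d/2 × |ln HR| − 1.96): d = 87 gives 51.3% and d = 84 gives 73.3%. With 1 year of accrual and 2 years of follow-up, Freedman's formula gives 53.8% and 75.2%. The stated range reproduces.

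**3. Excess with no drug toxicity.** Let c be the share of relapses with a new or worsened grade 3 or higher count. The documents give no value, so c = 25, 50 and 75% is assumed. Take all DFS events as relapses, each with a count, and no background cytopenia. The flagged share is c × (event share), and the excess on placebo is c × (0.15 to 0.20).

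| c | Placebo flagged | OCV-501 flagged | Excess on placebo |
|---|---|---|---|
| 25% | 12.0 of 60 (20%) | 9.0 to 9.8 (15 to 16%) | 3.7 to 5.0 points |
| 50% | 24.0 of 60 (40%) | 18.0 to 19.5 (30 to 33%) | 7.5 to 10.0 points |
| 75% | 36.0 of 60 (60%) | 27.0 to 29.3 (45 to 49%) | 11.2 to 15.0 points |

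If 90% of events are relapses, the excesses are 3.4 to 4.5, 6.7 to 9.0 and 10.1 to 13.5 points.

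**4. Adding background cytopenia.** Let μ be a yearly rate of grade 3 or higher cytopenia not due to relapse, equal in both arms (assumed 0 to 0.2), and λ = −ln(2-year DFS)/2, so 0.805 on placebo and 0.525 or 0.458 on OCV-501. With F = 1 − exp(−2(μ + λ)):
- background first: μ/(μ + λ) × F
- relapse first and flagged: c × λ/(μ + λ) × F

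Example with μ = 0.1, c = 50% and 35% DFS on OCV-501: placebo 0.092 + 0.372 = 0.464; OCV-501 0.114 + 0.300 = 0.414; excess on placebo 5.1 points from unrounded values.

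Across the 24 combinations (four values of μ, three of c, two of DFS), counting relapse values shifted the comparison in favour of the arm with fewer relapses every time. The net difference pointed that way in 22. In the other two (μ = 0.2, c = 25%) it was −0.4 points.

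**5. Why a cut alone is not enough.** Mean time before a DFS event within 2 years is (1 − DFS)/λ: 0.99 years on placebo, 1.24 to 1.31 on OCV-501. With relapse counts removed and μ between 0.05 and 0.2, OCV-501 shows 1.2 to 5.0 points more cytopenia from exposure alone. Per person-year the arms are equal by construction.

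**The case against.** Most of the case on the other side concerns size, and much of it stands.

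- The value of c is assumed. Relapse is called on any reappearance of blasts in blood or at least 5% in marrow (Protocol Table 7.2.1.1-1), with counts at least every two weeks, so many relapses may be caught before severe cytopenia. At c = 25% the excess is only 2 to 3 subjects of 60.
- Some events are deaths, and Protocol 7.1.4.2 allows withdrawal tests to be skipped after relapse. Both shrink the effect.
- Other outputs give a partial second view: laboratory tables by time point, listings with abnormal values flagged, and AE and adverse drug reaction tables by grade. They help a reader trace cases but do not correct the worst-grade tables.
- The tables are descriptive, and only haematology rows are affected. The documents report no dose-limiting toxicity in nine phase 1 subjects and no systemic toxicity up to 2.5 mg/kg in the intermittent-dose animal studies.

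A reader might infer that these tables would mainly show who relapsed, or that the arm with fewer relapses must look less myelotoxic. The documents support neither: they give no cytopenia rate, and longer exposure can offset the effect. A reader might also infer that the AE data are free of relapse effects. Protocol 8.1.1 sets aside only relapse without related comorbidity; a comorbidity with clinical symptoms that meets the AE definition is still reported.

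**Conclusion.** The point holds as a confounding of disease with drug effect that the SAP leaves unaddressed. Counts at or after relapse can set the worst haematology grade and carry a treatment-emergent label, while relapse alone is kept out of the AE tables.

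The spurious excess on placebo is about 4 to 15 points if OCV-501 performs as planned, c lies between 25 and 75%, every event is a relapse with a count available, and there is no background cytopenia. It is smaller when any of the last three conditions is relaxed, can be offset by longer exposure, and is nil if relapse rates do not differ. The direction of the shift is firm given unequal relapse; its size cannot be taken from the documents.

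It may be tempting to go further and replace the main tables with ones cut at the site-judged relapse date. The documents do not support that. The count that prompted the marrow would stay in, and the main DFS analysis uses central review (Protocol 11.3.1, SAP 4.7.1.1), which may not confirm every site call.

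**What to change.** Keep the all-values tables. Add to SAP 4.8.3:

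1. Parallel worst-grade and new-or-worsened haematology tables that use only post-baseline values before the relapse-defining sample. Define that sample as the blood or marrow sample, or the count that prompted the marrow, on which the site called relapse.
2. Exposure-adjusted rates by arm for these tables, because time at risk differs.
3. A flag in the laboratory listings on values from that sample onward.

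Record the addition in SAP 4.13. The site's event dates and sample dates are already in the CRF (Protocol 7.2.1.1).

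The cost is one extra set of tables. Two limits remain: some leukaemic counts before the relapse-defining sample stay in, and counts after a site-called relapse that central review does not confirm appear only in the all-values tables.
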